# 5.2 Limitations

Few caveats should be taken while generalizing findings of the study. First, the study was conducted in a single center; therefore, results would be different if such psychological disorders persist in parents of cancer children in other clinical or community setups. Further effect of parents' age and gender could not be found out in our study.

The MBT intervention alone could not help in reducing anxiety significantly. The reason would be most of the participants were anxious about finding a suitable residence in the city during treatment period for which researcher could not help. Also, this element was not addressed in the study questionnaire so that the reason would be confounded to determine sole effect of MBT intervention on anxiety too.

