#### 3.13.2 Independent Variable:

The independent variable was mentioned as socio-demographics and other information in **Annexure-I**. It included (1) Sectioned (A), Personal information focusing Child Age, Child gender, Primary Care taker area of residence, (2) Section (B), Socioeconomic and educational status of Childs caretaker focusing Occupation, Level of education, Employment status, Income per month and Treatment Expenses. (3) Section C, Cancer Information focusing Diagnoses, Type of cancer, Stage of cancer, treatment being sought, Duration of Chemotherapy, Date of diagnoses, Duration of diagnoses, Family History of cancer and Number of cancer patients in the family of the patient other than this case. (4) Section (D), Pain scale focusing Pain felt by the child at that moment and (5) Section (E), General information related to Anxiety and depression focusing, Caregivers awareness of whether he or she was anxious and depressed? Did caregivers taken any treatment sought for his anxiety and depression? Whether any health professional advices the Caregivers? and Do caregiver had smoking habits?

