**Figure 1: Participants selection** 

#### 4.2 Baseline data:

#### **Personal information**:

Total 31.2% (n=24) children were under 2-4 year of age, 23.4% (n=18) were under 5-7 years, 31.2 % (n=24) were also under 8-12 year of age and 14.3% (n=11) children were under 13-18 years of age group. Female to male ratio was 1:1.85. Majority (88.3%) of primary caregiver of studied children were any one of the parents. Most of them belonged to non-local area, other than Karachi territory.

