# Factor associated with Anxiety and depression:

Nearly, 42.9% parents had smoking habits, while 57.1 % did not have smoking habit. The baseline data of parents along with their child are shown in Table 1.

	Total	Intervention	Control	
Section A: Personal information	n=77 (100%)	n=41 (100%)	n=36 (100%)	Chi-Square
				P-Value
1. Child Age:	-	-	-	
2-4years	24(31.2)	13(31.7)	11(30.6)	0.98
5-7years	18(23.4)	10(24.4)	8(22.2)	
8-12 years	24(31.2)	12(29.3)	12(33.3)	
13-18 years	11(14.3)	6(14.6)	5(13.9)	
2. Child Gender:	50/54.0	0 4 ( 5 0 5 )		
Male	50(64.9)	24(58.5)	26(72.2)	0.20
Female	27(35.1)	17(41.5)	10(27.8)	
3. Primary Care Giver:	(0/00.2)	20(02.7)	20(02.2)	0.00
Mother/Father	68(88.3)	38(92.7)	30(83.3)	0.20
Other	9(11.7)	3 (7.3)	6 (16.7)	
4. Residency/Locality:	20(2( 4)	17(41.5)	11(20.6)	0.22
	28(36.4)	1/(41.5)	11(30.6)	0.32
Non-Local	49(63.6)	24(58.5)	25(69.4)	A1 • A
Section B: Socioeconomic and	N=77 (100%)	Intervention	Control	Chi-Square
educational status of Childs care taker		n=41 (100%)	n=36 (100%)	P-Value
5. Occupation	12(54.4)	24(59.5)	19(50)	0.74
	42(54.4)	24(58.5)	18(50)	0.74
Shopkeeper	17(22.1)	8(19.5)	9(25)	
Other	18(23.4)	9(22)	9(25)	
6. Level of education		11(2(0))	11(20.0)	0.00
	22(28.6)	11(20.8)	11(30.6)	0.80
School Education	33(42.9)	1/(41.5) 12(21.7)	16(44.4)	
Higher Education	22(28.6)	13(31.7)	9(25)	
7. Employment status	40((2, ())	29((9.2)	21(59.2)	0.26
Daily wages	49(63.6)	28(08.3)	21(58.5)	0.30
Nonthly Salary	28(36.4)	13(31.7)	15(41.7)	
8. Income per month (Rupees)	20(27.7)	12(20.2)	17(47.2)	0.10
less than 10,000	29(37.7)	12(29.3)	1/(4/.2)	0.10
More than 10,000	48(62.3)	29(70.7)	19(52.8)	
Section C. Concer Information	N = / / (100%)	n=41 (1009/)	Control	D Voluo
0 Diagnosos		II-41 (10070)	II-30 (100 % )	F-value
J. Diagnoses	51(66.2)	28(68.2)	22(62.0)	0.59
Othora	31(00.2) 26(22.8)	20(00.3) 12(21.7)	23(03.9) 12(26.1)	0.58
10 Family History of cancor	20(33.8)	15(51.7)	15(50.1)	
No.	70(00.0)	34(82.0)	33(01.7)	0.25
	70(90.9)	7(17.1)	3(83)	
Section D: Pain scale (Visual analog	N=77 (100%)	Intervention	S(0.5)	Chi Sauara
scale)		n=41 (100%)	n=36(100%)	P_Voluo
11 Pain falt by the child			II-30 (100 /0)	I - Value
No	49(63.6)	23(56.1)	26(72.2)	0.14
Ves	28(36 /)	18(43.0)	10(27.8)	
Section F: Factor associated with	N=77(100%)	Intervention	Control	Chi-Square
Anxiety and depression		n=41 (100%)	n=36(100%)	P-Value
12. Do parent have smoking habits?			1 20(10070)	I - V aiut

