8.	Income per month (Rupees)	0.32	0.07	0.92
9.	Diagnoses	0.97	0.77	0.81
10.	Family History of cancer	*0.02	0.20	0.77
11.	Pain felt by the child	0.12	0.11	0.51
12.	Do parent have smoking habits?	0.92	0.88	0.50
	Significant Association (P-V	/alue <0.05)		

 Table 5 : Association of Socio demographical features with pre-depression, pre-anxiety and pre-stress

The significant association has been identified between child age and pre-anxiety of parents, Occupation and pre-depression of parents and family history of cancer and pre-depression of parents. It is further identified that there is significantly 4 times more likely to have no Anxiety at the time of admission (pre-anxiety), if the child age is < 4 year as compared to the child age > 4 years [OR=4.1, 95%CI(1.0-16.2),P-Value=.042] Moreover, found that there is significantly 20% less likely to have no depression at the time of admission (pre-depression), if Family history has cancer as compared to no history of cancer patient in family [OR=0.20, 95%CI(.047-.880),P-Value=.033]. No association was found with other variable.

Since, almost all variables produced insignificant effect on the outcome variables at three stages of observations. Therefore, these variables were not proceeded for multivariable analysis.

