# 5.5 Conclusion:

There is a positive effect of nurse-led multimedia education, booklet providence and telephonic follow up about chemotherapy and side effects management on parent's depression and stress of children receiving chemotherapy showing in this study for the first time in Pakistan. For anxiety reduction, other strategies should also be incorporated.

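### Section 5.2 explains the anxiety null by a lodging worry said to confound the MBT effect; nothing in the report supports this, and the P value of 0.172 fits a test that averages in the pre-treatment visit

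*Combined protocol and SAP*

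**What the plan says.** Section 4.3.3 and Table 4 report no significant anxiety difference between groups (P=0.172). Section 5.2 offers one reason, that "most of the participants were anxious about finding a suitable residence in the city during treatment period for which researcher could not help", and adds that "this element was not addressed in the study questionnaire so that the reason would be confounded to determine sole effect of MBT intervention". The Abstract and Section 5.5 then conclude: "For anxiety reduction, other strategies should also be incorporated".

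Three other places bear on this.

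- Section 3.13.2 lists "Primary Care taker area of residence" among the baseline items. Table 1, item 4, reports it by arm as local or non-local.
- Table 5 gives P=0.58 for residency against pre-intervention anxiety. After naming three significant pairs, none involving residency, the text below it says "No association was found with other variable".
- The same text says that the covariates were not carried into multivariable analysis because almost all had non-significant effects.

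Section 3.14 specifies a one-way repeated-measures ANOVA over time with post hoc comparisons between visits. It does not define the between-group test behind the 0.172.

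**The concern.** Section 5.2 gives readers a cause for the anxiety result that was neither counted nor tested, and describes it as confounding. Confounding of a randomised comparison needs a factor that differs between arms, and the section gives no evidence that lodging worry did. The one recorded variable close to it is not mentioned there and entered no adjusted model.

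More is at stake than wording. The explanation takes it as settled that MBT did not reduce anxiety relative to control. If the null comes from how the group effect was tested, there may be no null to explain, and the anxiety conclusion in the Abstract and Section 5.5 would need to change.

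**Working it through.** Differences are MBT minus control unless stated. Negative means less anxiety with MBT.

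**1. Residency by arm (Table 1, item 4).** Local 17/41 and 11/36; non-local 24/41 and 25/36.
- Pearson chi-square = 77 × (17×25 − 24×11)² / (28×49×41×36) = 0.986, P=0.321. This reproduces the printed 0.32.
- Non-local: 58.5% − 69.4% = −10.9 percentage points, 95% CI −32.2 to +10.4.

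**2. Residency and baseline anxiety (Table 5, P=0.58).** The margins are 28 local and 49 non-local families (Table 1), with 52 anxious and 25 not (Table 3). Only one whole-number table with these margins gives 0.58: local 20/28 anxious (71.4%), non-local 32/49 (65.3%).
- Chi-square = 77 × (8×32 − 20×17)² / (28×49×25×52) = 0.305, P=0.581.
- Non-local minus local: −6.1 points, 95% CI −27.5 to +15.3.
- Power was about 44% for a true 20-point difference and 77% for 30 points. The result is no detected association; it does not show absence of one.

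**3. What the imbalance could do.** If non-local status adds g DASS anxiety points (g is an assumption), the arm contrast shifts by g × (24/41 − 25/36) = −0.109g. For g = 2, 5 and 10 the shift is −0.22, −0.55 and −1.09 points, flattering MBT. If g is negative, as the table in step 2 weakly suggests, the shift is against MBT.

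**4. Reproducing P=0.172.** Table 2, anxiety, mean (SD):

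| Visit | MBT, n=41 | Control, n=36 | Difference |
|---|---|---|---|
| Pre (day 0) | 11.90 (6.51) | 10.72 (7.00) | +1.18 |
| Post (day 14) | 4.20 (3.43) | 6.61 (5.23) | −2.41 |
| 2-week post (day 28) | 1.75 (2.33) | 4.27 (3.61) | −2.52 |

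- Average over three visits: (1.18 − 2.41 − 2.52)/3 = −1.25.
- The variance of a parent's three-visit average is (1/9) × the sum over visit pairs of SDi × SDj × ρ, with ρ replaced by 1 when i=j. The within-person correlation ρ is not reported and is assumed.
- At ρ=0.5: MBT 11.67, control 18.91; pooled (40×11.67 + 35×18.91)/75 = 15.05; SE = √[15.05 × (1/41 + 1/36)] = 0.886; t = −1.25/0.886 = −1.41 on 75 df; P=0.162.
- At ρ=0.6 the same steps give P=0.181. The printed 0.172 lies between.
- Over the same ρ range, this calculation gives 0.011 to 0.015 for depression and 0.009 to 0.012 for stress. Table 4 prints 0.012 for both.
- Table 4's anxiety drops of 5.90 and 8.29 match equally weighted arm averages: [(11.90−4.20) + (10.72−6.61)]/2 = 5.905 and [(11.90−1.75) + (10.72−4.27)]/2 = 8.30. That fits a model with arm and visit as factors, whose group line is this three-visit average.

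**5. Anxiety at follow-up.**
- Day 14: −2.41; SE = √(3.43²/41 + 5.23²/36) = 1.023; Welch P=0.022.
- Day 28: −2.52; SE = √(2.33²/41 + 3.61²/36) = 0.703; Welch P=0.0007.
- Difference in change to day 28: −2.52 − 1.18 = −3.70, with P from 0.031 (ρ=0) to 0.002 (ρ=0.75).
- A baseline-adjusted day-28 difference equals −2.52 − 1.18β, where β is the slope on baseline. For β between 0 and 1 it lies between −2.52 and −3.70.
- Anxious, yes/no (Table 3): 6/41 vs 15/36 at day 14 (chi-square P=0.008); 2/41 vs 11/36 at day 28 (Fisher P=0.005).

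**The case against.** The best defence is that Section 5.2 is tentative and literally correct on measurement. It says that worry about finding lodging was not in the questionnaire, and no listed item covers it. Local or non-local status is only a proxy. A reader might infer that the baseline table contradicts the section; it does not.

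A reader might also infer that residence is unrelated to anxiety. P=0.58 on 28 against 49 families cannot show that. It also concerns anxiety before the intervention, whereas Section 5.2 speaks of the treatment period.

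A third tempting inference is that the residency imbalance favours MBT outright. That holds only if non-local families are more anxious. The one table that fits P=0.58 has local parents slightly more anxious, which would turn the imbalance against MBT. The imbalance is in any case compatible with chance, and Table 1 covers completers rather than everyone randomised.

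Finally, a stressor outside the reach of the education could blunt its effect without confounding anything. This stands as a hypothesis. It does not rescue the word confounded, and no data are offered for it.

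**Conclusion.** The confounding statement is unsupported. A worry shared by both arms does not bias the contrast. On Section 5.2's own premise that needing lodging raises anxiety, the recorded imbalance works in the wrong direction to hide a benefit, and by no more than about 1.1 points even at an assumed 10-point effect.

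The printed P=0.172 is consistent with a group effect of −1.25 points averaged over all three visits, in which the 1.18-point higher MBT baseline offsets part of the later benefit. The follow-up differences are 2.41 and 2.52 points in MBT's favour. This rests on the Table 2 arm values and on assumed correlations of 0.5 to 0.6; the model output is not shown, so the match is strong but not proof.

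A reader might go further and infer that MBT has been shown to reduce anxiety. The documents do not support that: the by-visit tests are post hoc, and they use 77 of 100 randomised parents, with 9 lost in MBT and 14 in control.

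**What to change.** - Delete the statement that lodging worry confounds the MBT effect. Remove the lodging explanation, or label it as speculation without data.
- State that residency was collected, give its distribution by arm (24/41 vs 25/36 non-local, P=0.32), and say that no association with baseline anxiety was detected (P=0.58), with the low power noted.
- Name the model behind the between-group P values. Report anxiety at day 14 and day 28 by arm, adjusted for baseline anxiety, with confidence intervals; or report the group-by-time interaction. Add residency as a sensitivity covariate and label the analysis post hoc.
- Revise the anxiety conclusion in the Abstract and Section 5.5 to match, stating the completer basis and the unequal losses.
- A split by residence (17 vs 11 local, 24 vs 25 non-local) is optional and too small to inform.

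The cost is one model on data already held and a rewritten paragraph. The drawback is that the model is chosen after the results are known, and it may change the stated anxiety conclusion.

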#### 5.3 Strength of study:

There are certain strengths to report about this study. First, the study was of its first kind to report major psychological disorders among caregiver of cancer children in Pakistan. The novel internationally adapted MBT intervention showed noteworthy decline which added the strength that the intervention is replicable to reduce depression, anxiety and stress among target population. The higher reliability scores also strengthened the confidence in using the MBT intervention for the same.

Furthermore, despite having loss to follow-up, we retained more than desired sample size in both groups which yielded good power of the study.

# 5.5 Conclusion:

There is a positive effect of nurse-led multimedia education, booklet providence and telephonic follow up about chemotherapy and side effects management on parent's depression and stress of children receiving chemotherapy showing in this study for the first time in Pakistan. For anxiety reduction, other strategies should also be incorporated.

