#### Methodology:

A randomized control trial was conducted in the department of chemotherapy at Department of Pediatric Oncology at Indus hospital, Karachi from September-December 2018 on parents of children below 18 years of age undergoing chemotherapy for the first time. Total 100 parents were randomly divided into Intervention group (n=50) and Control Group (n=50). After excluding lost to follow up, the data was analyzed from 77 sample of parents (41 in intervention group and 36 in control group). The intervention group received multimedia education, booklet and weekly tele-nursing follow-up about chemotherapy and side effects management. The control group received routine care. Parent's anxiety, depression and stress were identified by using DASS-21 and repeated measures ANOVA was used to observe changes in outcomes over study period.

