#### Result

Total 63.4% (n=48) children were under 12 years of age and 64.9% (n=50) children were male. Majority of the parents were non-residence of Karachi, labor and low education and income. 66.2% (n=51) children diagnosed with leukemia, 63.6% (n=49) children had no pain. At the baseline, depression was found in 84.4% (n=56) parents while 67.5% (n=52) parents were anxious and 55.8%(n=43) parents had stress, After the MBT intervention, significant reductions were observed in depression and stress (P-Value <0.05) of the parents in MBT group. A sharp decline was observed just after one week while at final stage intervention group showed higher decrease in depression and stress while anxiety was observed insignificantly different in both groups,

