#### 3.7 Sample Size:

By using NCSS PASS v.11 repeated measure analyses of variance (RMANOVA), at 80% power, and 95% confidence interval., RMANOVA of STAI Anxiety score for interventional group at Pre-Intervention means 42.01 (SD=12.96), Post intervention means 37.27 (SD=13.47) and 2 weeks post intervention means 38.40 (SD=10.55) [11], The sample size calculated was 30 samples per group. After adjusting error in non-response of data collection 50 samples were drawn from each group. Total 100 caregivers along with their children was recruit in this study.

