#### 4.3.3 Changes in depression, anxiety and stress scores over different periods:

Table 4 depicted significance values from RM-ANOVA and further post-hoc analyses. Profile plots mentioned as figure 2-4 displayed changes of mean scores of depression, anxiety and stress at baseline, post and 2-week post intervention.

**Depression**: The average depression between intervention and control group was significantly different (P=0.012) over study period (P<0.0001). Post-hoc analysis revealed that a reduction of 7.76 unit decrease in depression score from baseline to post intervention while it significantly reduced to 11.47 unit after 2 weeks of the study.

**Anxiety**: The anxiety level did not show any significant difference between intervention and control group (P=0.172) though both groups displayed concurrently significantly decline in anxiety level at pre, post and 2 week post study period (P<0.0001). Post-hoc analysis also discovered that a reduction of 5.90-unit reduction in Anxiety score from the reference line after intervention and significantly reduced to 8.29 unit after 2 weeks of the study.

**Stress**: The reduction in stress level depicted similar panorama as it was observed in depression score. Post-hoc analysis further exposed a decrease of 7.67-unit reduction in stress score from the baseline line after MBT intervention and significantly reduced to 11.79 units after 2 weeks of the study.

Denendent	Significance value between study groups	Significance value over time	Post Hoc Analysis P-Value with Mean differences		
Variables			Pre & Post	Pre & 2week Post	Post & 2week Post
Depression	0.012	<0.0001	<0.0001 Dif. (7.76)	<0.0001 Dif. (11.47)	<0.0001 Dif. (3.70)
Anxiety	0.172	<0.0001	<0.0001 Dif. (5.90)	<0.0001 Dif. (8.29)	<0.0001 Dif. (2.38)
Stress	0.012	<0.0001	<0.0001 Dif. (7.63)	<0.0001 Dif. (11.79)	<0.0001 Dif. (4.15)

Figure 3: Anxiety scores of intervention and control

Block

-Intervention -Control

 Table 4:
 Significant values of depression, anxiety and stress scores

Figure 4: Stress scores of intervention and control group during study period

	socio demographical features	Pre-Depression Chi-Square P-Value	Pre-Anxiety Chi-Square P-Value	Pre-Stress Chi-Square P-Value
1.	Child Age	0.58	*0.031	0.18
2.	Child Gender	0.42	0.15	0.35
3.	Primary Care Giver	0.69	0.41	0.46
4.	Residency/Locality	0.67	0.58	0.10
5.	Occupation	*0.017	0.25	0.20
6.	Level of education	0.13	0.25	0.15
7.	Employment status	0.28	0.96	0.76

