# 5.6 Recommendation:

Nurse-led multimedia education, booklet providence and telephonic follow up about chemotherapy and side effects management can be recommended as supportive care to reduce parent's depression and stress of children receiving chemotherapy for the first time.

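### Anxiety is set apart from depression and stress only because its between-group p-value was 0.172 rather than 0.012; no interval or cross-outcome comparison supports the contrast, and the post-intervention scores do not show it

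*Combined protocol and SAP*

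**What the plan says.** Section 4.3.3 reports that "The anxiety level did not show any significant difference between intervention and control group (P=0.172"), against P=0.012 for depression, and Table 4 gives 0.012 for stress as well. These three p-values are the only between-group statistics for the DASS scores. Section 3.14 plans a repeated-measures ANOVA over the three visits. It mentions no between-arm interval, margin or comparison of one outcome with another.

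Four places then treat anxiety differently from the other two outcomes:

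- Abstract (Conclusion) and 5.5: a positive effect on depression and stress, followed by "For anxiety reduction, other strategies should also be incorporated".
- 5.2: "The MBT intervention alone could not help in reducing anxiety significantly". Worry about finding somewhere to live is offered as the reason, and the text concedes that the questionnaire did not cover it.
- 5.6: MBT "can be recommended as supportive care to reduce parent's depression and stress of children receiving chemotherapy for the first time"; anxiety is absent.

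The opening of Chapter 5 repeats the contrast. Other parts of the document go the other way. The Chapter 5 discussion of MBT as a nursing intervention describes a significant fall in anxiety and ends by saying that MBT would help with all three outcomes. Section 5.3 calls MBT replicable for all three, and 5.10 recommends it for anxiety as well.

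**The concern.** Two inferences are made from p-values alone. First, a non-significant anxiety result is used to say that MBT needs supplementing for anxiety, with no look at which effects the data still allow. Second, significance on two outcomes and non-significance on a third is treated as a difference between outcomes, although that difference was neither estimated nor tested. If neither step is sound, the outcome-specific part of the conclusion and recommendation has no support, and services could set MBT aside for anxiety without evidence for doing so. Because the document also recommends MBT for anxiety elsewhere, a reader cannot tell which message the trial supports.

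**Working it through.** **Inputs.** Table 2 means and SDs by arm (n = 41 and 36, so 75 df) and the Table 4 p-values. Differences are intervention minus control, so a negative value favours MBT.

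| | Baseline | Post | Two-week post | Average of three |
|---|---|---|---|---|
| Depression | -0.87 | -3.28 | -3.48 | -2.54 |
| Anxiety | +1.18 | -2.41 | -2.52 | -1.25 |
| Stress | -0.04 | -3.98 | -3.95 | -2.66 |

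**Reproducing Table 4.** The between-group test in a two-arm, three-visit repeated-measures ANOVA equals a t test on each person's average over the visits. With the Table 2 SDs and an assumed common within-person correlation of 0.5 to 0.6 (not given in the documents), p is 0.011 to 0.015 for depression, 0.162 to 0.181 for anxiety and 0.009 to 0.012 for stress. The printed values are 0.012, 0.172 and 0.012. The unweighted arm means also give the Table 4 post-hoc differences within rounding (for anxiety 5.905, 8.30 and 2.395 against 5.90, 8.29 and 2.38). The printed p-values therefore fit a test on an average that includes baseline.

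**Intervals implied by the printed p-values.** SE = |difference| / t(p, 75 df); CI = difference ± 1.992 × SE.

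- Anxiety: 1.25 / 1.379 = 0.906; CI -3.06 to 0.56.
- Depression: 2.54 / 2.575 = 0.99; CI -4.51 to -0.58.
- Stress: 2.66 / 2.575 = 1.03; CI -4.71 to -0.60.

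The anxiety interval contains both -2.54 and -2.66.

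**Is anxiety different from the others?** The gaps are 2.54 - 1.25 = 1.29 points (depression) and 2.66 - 1.25 = 1.41 (stress). The SE of a gap is sqrt(SE1² + SE2² - 2r·SE1·SE2), where r, the correlation between the two effect estimates, is unknown.

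| Assumed r | p, anxiety vs depression | p, anxiety vs stress |
|---|---|---|
| 0 | 0.34 | 0.31 |
| 0.5 | 0.18 | 0.15 |
| 0.7 | 0.08 | 0.07 |
| 0.8 | 0.035 | 0.027 |

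**What baseline does to the average.** For anxiety, (1.18 - 2.41 - 2.52) / 3 = -1.25. Baseline imbalance alone supplies (1.18 + 0.87) / 3 = 0.68 of the 1.29-point gap from depression.

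**Post-intervention anxiety (pooled SD, unadjusted).**

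- Post: pooled SD 4.36, SE = 4.36 × sqrt(1/41 + 1/36) = 1.00; difference -2.41, CI -4.40 to -0.42, p = 0.018.
- Two-week post: pooled SD 3.00, SE 0.68; difference -2.52, CI -3.88 to -1.16, p = 0.0004.
- Two-week standardised differences: anxiety -0.84, depression -0.87, stress -0.94.
- Table 3, anxiety present at the last visit: 2/41 against 11/36, Fisher p = 0.005.

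**Extra fall from baseline to the last visit.**

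- Anxiety: (11.90 - 1.75) - (10.72 - 4.27) = 3.70.
- Depression: (15.41 - 2.63) - (16.28 - 6.11) = 2.61.
- Stress: (16.63 - 2.88) - (16.67 - 6.83) = 3.91.

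At an assumed pre-post correlation of 0.5, p is 0.007 for anxiety, 0.053 for depression and 0.003 for stress. On that contrast the same p < 0.05 rule would have left out depression, not anxiety.

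**The case against.** The strongest reply is that the text is milder than it first looks. Section 5.5 says other strategies should *also* be used; 5.2 says MBT *alone* did not reduce anxiety *significantly*; 5.6 omits anxiety without calling MBT ineffective for it. A reader might infer that the document declares anxiety unresponsive to MBT. It does not, and 5.3, 5.10 and the Chapter 5 discussion of MBT say the reverse. That stands. The fault is an unsupported contrast and an internal inconsistency, not a uniform claim of no effect.

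A reader might also want to call the anxiety result simply inconclusive, quoting -1.25 (-3.06 to 0.56). That figure mixes in the pre-intervention score, so it is not a clean treatment effect; printing it as the finding would replace one misleading statement with another.

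Nor do the documents support a claim that anxiety responds as well as the other outcomes. The visit-averaged anxiety estimate is about half the others, and a direct comparison could reach p < 0.05 if r were about 0.8.

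Finally, it is tempting to argue from low power, or from anxiety being the outcome on which the trial was sized. The documents state no between-arm effect size to power against. Section 3.7 used STAI scores over time in an intervention group, not a between-arm DASS-21 difference. Neither argument is needed.

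**Conclusion.** The contrast between anxiety and the other two outcomes is unsupported as written. It rests on one p-value above 0.05 and two below. On the document's own test the anxiety interval includes the effects called positive for depression and stress, and the outcomes were never compared. After intervention, the Table 2 differences favour MBT on anxiety at both visits, by about 2.4 to 2.5 points, with a last-visit standardised difference close to those of the other outcomes.

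The limits are these. The interval around -1.25 is reconstructed, on the reading that Table 4 tests the average over three visits, two-sided. The post-intervention figures are unadjusted, carry no multiplicity correction and cover the 77 completers of 100 randomised (9 lost from intervention, 14 from control). They show that the anxiety-specific message is hard to defend; they do not by themselves establish an effect on anxiety. The by-arm values in Table 2 were used because the anxiety total for the last visit is unreliable: 4.3.2 prints the depression figure (4.26 ± 4.36), while Table 2 prints 2.98 against (41 × 1.75 + 36 × 4.27) / 77 = 2.93.

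**What to change.** 1. For depression, anxiety and stress alike, report the between-arm difference at each post-intervention visit with its 95% CI, adjusted for the baseline score (or the group-by-time contrast), and state that it covers the 77 completers.
2. Base the anxiety wording on those estimates, not on p = 0.172 or the baseline-inclusive 1.25 points.
3. Remove the anxiety-versus-depression-and-stress contrast from the Abstract, 5.2, 5.5 and 5.6. If a smaller effect on anxiety is to be claimed, test it directly, for example as an arm-by-outcome term on standardised scores in one multivariate model. If a lack of effect is to be claimed, require the interval to exclude a stated margin.
4. Reconcile these sections with the opening of Chapter 5, its discussion of MBT as a nursing intervention, 5.3 and 5.10, so that the document carries one message on anxiety.

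The cost is three short analyses of data already held and some rewording. The price is a less clear-cut message by outcome, still limited to completers.
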